6.3 SAS Imputation Procedures

SAS PROC MI procedure will be used to perform imputations of the missing primary variables, namely, the PI and GI indices. The EM algorithm assumes multivariate normal distribution for the data; PI and GI values (baseline values included). The missing data for a given treatment group will be imputed independently with input data being the PI and GI data at all time points (baseline, 3 months and 6 months) from only that treatment group. The imputation procedure is valid when the missing data are missing at random. %MULTINORM macro can test for multivariate normality and PROC MI can display patterns of missing data.

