5.2 Intent-To-Treat Population

The intent-to-treat (ITT) data set will be the primary efficacy data set and will include all subjects randomized to a treatment group. Subjects will be analyzed in the group to which they were randomly assigned. Subjects with missing post-baseline PI and/or GI data will be included in the ITT analysis using appropriate input data sets and imputation methods. The Expectation-Maximization (EM) algorithm will be used, and this procedure assumes the data will be multivariate normal and missing at random. If these assumptions prove to be violated, other methods will be considered.

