5.3 Per-Protocol Population

A second per-protocol (PP) data set will be defined excluding any subjects with major deviations or lack of compliance with taking their assigned study treatment. The PP dataset will be used only for the primary efficacy analysis (3M oral rinse vs. vehicle control) and the secondary efficacy analysis with all four treatment groups.

The following major protocol deviations will lead to exclusion from the per protocol data set:

- (1) Subject who is missing either one or both primary endpoints of GI and PI values at 6 months
- (2) Subject who did not meet the inclusion criteria of baseline Gingival Index (GI) score of ≥ 1.0 and a baseline Plaque index (PI) score of ≥ 1.5 .
- (3) Subject with $< 80\%$ of planned dose (or alternatively $>20\%$ of no rinsing).
- (4) Subject with ≥ 3 consecutive days of no rinsing within 4 weeks prior to PI and GI assessments.
- (5) Subject who indicated antibiotics, anti-inflammatory, anticoagulants, or immunosuppressant drug use, regardless of dose, within 6 weeks prior to PI and GI assessments.

All deviations not captured above that will result in exclusion from the PP analysis will be defined and justified in a blinded fashion. In addition, documentation will be made of these data classification decisions prior to data lock.

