6.1 Determination of Sample Size

The sample size was estimated based on GI and PI scores from preliminary clinical study data and the literature. It is estimated that 34 subjects per group will provide 90% power to detect a difference of 0.40 (standard deviation of 0.5) in the GI and PI scores using a 1-sided 0.025 alpha level. To account for possible dropouts, a sample size of 50 subjects per group will be recruited.

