6.2 Handling of Dropouts and Missing Data

Subjects with missing PI and/or GI data will be included in the ITT analysis using appropriate input data sets and imputation methods. It is assumed that the data will be multivariate normal and missing at random, and Expectation-Maximization (EM) algorithm will be used. If this assumption proves to be unreliable, other methods will be considered. In addition, a sensitivity analysis using alternative imputation methods to handle the missing data, namely last observation carried forward and using group means, will be conducted to examine the robustness of the primary analysis.

If a subject becomes pregnant during the study, the subject will be discontinued, and assessments completed.

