8. EFFICACY ANALYSIS

8.1 Primary Efficacy Analysis (3M Oral Rinse vs. Vehicle Control)

Performance of the 3M Oral Rinse will be assessed based on two primary endpoints. Statistical analysis will be performed on the PI and GI scores at 6-months using an ANCOVA with treatment as the factor and baseline score as a covariate. The success criterion for the study will be based on the single comparison between the 3M Oral Rinse group and the vehicle control group. The primary efficacy analysis will exclude data from the other two treatment groups, namely, the PerioShield (predicate) and the water control groups.

Significance of the overall treatment effect will be assessed by the p-value associated with the F-test statistic for the treatment group. The level of significance will be two-sided alpha of 0.05. The main null hypothesis of interest to support that 3M Oral Rinse reduces plaque and gingivitis is as follows:

$$H_0: \mu_{3M \text{ Oral Rinse}} \geq \mu_{\text{Vehicle}} \text{ versus } H_A: \mu_{3M \text{ Oral Rinse}} < \mu_{\text{Vehicle}}$$

Both primary endpoint comparisons will be based on the intent-to-treat (ITT) data set. The study will be considered successful if both primary endpoints are met.

In the event of a significant demographic or baseline variable, the primary efficacy ANCOVA model will be expanded to include this significant variable as a covariate or factor in the model. Statistical models with interaction terms or subgroup analyses will be explored if appropriate to help further understand the treatment effect.

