11.7 Missing Data

Subjects with missing PI and/or GI data will be included in the ITT analysis using appropriate input data sets and imputation methods. It is assumed that the data will be missing at random, and Expectation-Maximization (EM) algorithm will be used. If this assumption proves to be unreliable, other methods will be considered. In addition, a sensitivity analysis using alternative imputation methods to handle the missing data, namely last observation carried forward and using group means, will be conducted to examine the robustness of the primary analysis.

If a subject becomes pregnant during the study, the subject will be dropped and assessments completed.

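### The primary ITT test rests on EM imputation with no draws, number of imputations or pooling rule; if done as one fill, its p-value is too small

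*SAP*

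**What the plan says.** The ITT set is primary and holds every randomised subject. For missing scores, SAP 5.2 states: "The Expectation-Maximization (EM) algorithm will be used, and this procedure assumes the data will be multivariate normal and missing at random". Protocol 11.7 agrees: "It is assumed that the data will be missing at random, and Expectation-Maximization (EM) algorithm will be used". SAP 6.3 adds the software: "SAS PROC MI procedure will be used to perform imputations of the missing primary variables, namely, the PI and GI indices". Imputation is done separately in each arm, from PI and GI at baseline, 3 and 6 months.

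The test is in SAP 8.1: "Significance of the overall treatment effect will be assessed by the p-value associated with the F-test statistic for the treatment group". The model is an ANCOVA with baseline as covariate, at two-sided 0.05, and "The study will be considered successful if both primary endpoints are met".

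The supporting analyses are "a sensitivity analysis using alternative imputation methods to handle the missing data, namely last observation carried forward and using group means" (SAP 6.2) and a per-protocol set that drops any "Subject who is missing either one or both primary endpoints of GI and PI values at 6 months" (SAP 5.3). Other methods come into play only if multivariate normality or missing-at-random fails.

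No dropout rate is stated. The only guide is SAP 6.1, which needs 34 per group and adds: "To account for possible dropouts, a sample size of 50 subjects per group will be recruited". Protocol 11.8 says dropouts are not replaced.

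**The concern.** EM estimates means and covariances. Used once to fill gaps, it puts each missing score at its predicted value, with no residual scatter and no allowance for error in the prediction. An ordinary ANCOVA then counts 50 measured subjects per arm when there are fewer, and sees less scatter than exists. Both effects shrink the standard error.

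The text never says that the fill is single, and PROC MI can produce multiple draws. But SAP 6.3, the section devoted to imputation, stops at the algorithm, its inputs and its assumptions, and SAP 8.1 names no pooled test. Two analysts could follow the plan faithfully and report different deciding p-values. The fallback to other methods does not help, because an understated standard error arises even when normality and missing-at-random both hold.

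The amount to be imputed is also open. The protocol provides for assessment at discontinuation (synopsis schedule, 6.6, 8.1.6) and for using existing data from withdrawn subjects (13.1). It does not say whether such a score is analysed as the 6-month score.

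**Working it through.** **Inputs from the documents.** 34 per group needed, 50 recruited; difference 0.40; SD 0.5; 90% power; one-sided 0.025 for sizing (SAP 6.1). ANCOVA on baseline, two-sided 0.05, both endpoints required (SAP 8.1).

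**The plan's own figure.** The normal approximation gives n = 2 × (1.960 + 1.282)² × (0.5/0.40)² = 32.8, so 33. The exact t-test gives 89.3% power at 33 and 90.2% at 34, so 34 is reproduced. The largest loss that still leaves 34 is 1 − 34/50 = 32%.

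**Size of the understatement by hand.** Let a fraction f be missing at random in each arm and filled from that arm's regression on baseline. The filled points lie on the line, so the residual variance is estimated as about (1 − f)σ² and is divided by the full n.

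- Reported SE ≈ √[2(1 − f)σ²/n]
- True SE ≈ √[2σ²/((1 − f)n)]
- Ratio ≈ 1 − f
- Two-sided error ≈ 2Φ(−1.96(1 − f))

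| Missing | Ratio | Two-sided error | One-sided error |
|---|---|---|---|
| 6% | 0.94 | 6.5% | 3.3% |
| 10% | 0.90 | 7.8% | 3.9% |
| 20% | 0.80 | 11.7% | 5.8% |
| 32% | 0.68 | 18.3% | 9.1% |

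This ignores what the 3-month and other-index scores add, so simulation is needed.

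**Simulation of one EM fill.**

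- 50 per arm, SD 0.5, equal random dropout in both arms, about half of it before month 3, no exit-visit score.
- Assumed correlations: baseline to later 0.4, 3 to 6 months 0.6, GI with PI 0.4. Variants for the first two: 0.2/0.3, 0.3/0.8 and 0.6/0.8 (ranges in brackets).
- Success means both p < 0.05 in favour of the rinse.
- 16,000 trials per rate in the main case and 8,000 per variant. The Monte Carlo SE on 3.3% is about 0.14 points.

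| | 6% | 10% | 20% | 32% |
|---|---|---|---|---|
| Error per endpoint (nominal 5%) | 6.5 (6.1–6.7) | 7.4 (6.8–7.9) | 10.5 (9.4–11.4) | 16.0 (13.1–17.9) |
| False success, PI better by 0.40, GI null (nominal 2.5%) | 3.3 (2.8–3.4) | 3.9 (3.3–4.0) | 5.1 (4.9–5.8) | 7.8 (6.8–8.4) |
| False success, both null | 0.5 | 0.6 | 1.0 | 1.7 |

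Reported over true SE is 0.95 at 6% and 0.91 at 10%. The 20% and 32% columns are an outer range, not a forecast.

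A separate simulation with other correlations (0.3/0.5, 0.5/0.7, 0.7/0.85) and dropout timings (half or all before month 3) gave an error per endpoint of 6.0–7.0%, 7.1–8.7%, 9.8–12.0% and 13.9–18.8%. Complete cases stayed at 4.4–5.5% throughout.

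**The planned checks at 6–10% missing, main case.**

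- Group-mean fill: error 6.6–7.7%, false success 3.4–3.9%. It has the same flaw, and it contradicted only 12–15% of the false EM successes.
- Last observation carried forward: error 4.9–5.0%, false success 2.4–2.7%. It contradicted 30–35% of them.
- Complete cases: error 5.0%, false success 2.5–2.6%.

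**Pooled multiple imputation** (20 monotone-regression imputations by arm, Rubin's rules, 2,500 trials per rate) gave an error of 5.2 / 4.1 / 4.7 / 3.9% and false success of 2.4 / 2.0 / 2.6 / 1.8% at 6 / 10 / 20 / 32% missing. It is not inflated.

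**The case against.** The strongest reply is that the harm depends on a reading the text does not state. SAP 6.3 speaks of imputations in the plural and names a procedure built for multiple imputation. That stands: what is established is an unspecified step in the deciding analysis, and every error rate above is conditional on one fill.

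Next, the missing rates, correlations and equal random dropout are not document figures, and at 6% missing the effect is small. The lowest variant, 2.8%, has a Monte Carlo SE of about 0.18 points and cannot be told apart from 2.5%. When neither endpoint works, requiring both keeps false success at 0.5–0.6%. All of this is true. The joint rule does not protect the case where one endpoint works and the other does not.

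The carried-forward check may catch more than 30–35% of false successes. Baseline is scored before a professional cleaning (protocol 8.2.2), so scores may fall afterwards. With an assumed common fall of 0.3–0.8 in both indices, the share at 10% missing rose to 42–49% but barely moved at 6%. These shares are fragile and the conclusion does not rest on them. Neither that check nor the per-protocol set decides success, and no rule covers disagreement.

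Finally, the plan's 90% power is per endpoint, so judging the fix by joint power is a stricter yardstick than the plan set. The cost is given below on that basis because success needs both endpoints.

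**Conclusion.** The concern holds. The primary analysis lacks the step that makes imputation valid for testing, and no other provision in either document supplies it. On the nearest literal reading the deciding p-value is too small. At an assumed 6–10% missing the inflation is modest: about 6.5–7.4% per endpoint against 5%, and 3.3–3.9% false success against 2.5% when only one endpoint works. At the 32% loss that the sample size allows, the error per endpoint would be about three times nominal.

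If multiple draws with pooling were intended, the inflation disappears and only the omission remains. If exit-visit scores count as month 6, the rate that applies is the share still missing: with 10% dropout and 40% of dropouts assessed at exit, 10% × (1 − 0.40) = 6%. The point should be fixed before unblinding. Confidence is medium because the reading and the missing rate are both open.

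**What to change.** In SAP 5.2, 6.2 and 6.3, specify multiple imputation by arm in PROC MI (MCMC or monotone regression) with a stated number of imputations and seed. In SAP 8.1, fit the ANCOVA to each completed data set and make the treatment contrast pooled by Rubin's rules (PROC MIANALYZE) the primary test. A likelihood-based repeated-measures model with baseline as covariate is an alternative. State whether a discontinuation-visit score is analysed as the 6-month score. The two planned sensitivity fills can stay, but agreement of the group-mean fill should not be read as evidence of robustness. Delta-adjusted imputation is optional.

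The cost is a few lines of text and code, with no change to conduct; SAP 1 allows amendment before unblinding. Standard errors widen against the EM fill by 7–8 / 12–13 / 26–30 / 48–56% at 6 / 10 / 20 / 32% missing. Joint power for a true 0.40 on both endpoints (assumed baseline correlation 0.2–0.4; 1,500 trials per cell) compares as follows:

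| | 6% | 10% | 20% | 32% |
|---|---|---|---|---|
| Pooled imputation | 95.9–97.5% | 93.3–96.6% | 86.3–93.2% | 76.3–85.6% |
| Complete cases | 96.3–97.7% | 94.5–96.6% | 89.1–93.5% | 83.3–88.7% |

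The sample size absorbs the correction at 6–10% missing but not fully at 20–32%, where pooled imputation by arm is also somewhat less powerful than complete cases.

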6.4 Training and Calibration of Clinical Examiner in the GI and PI Measures

The clinical examination of the GI and PI will be performed by experienced examiners who have publications on the GI and PI evaluation, and the examiners will perform the same clinical examination throughout the study. To ensure adequate reliability and consistency, a training and calibration session on the GI and PI evaluation will be conducted for the examiners prior to the baseline, 3-month, and 6-month visits.

The training and calibration will be conducted using digital dental photographs of 15 historical subjects selected from a library at the study site. The digital dental photographs of 15 subjects will be selected to provide adequate representation of the full range of the GI (0 to 3) and PI (0 to 5) scales. In addition, the goal will be to achieve a sample that is representative of the study population in terms of race, age and sex. The digital dental photographs instead of subjects are used for training and calibration because clinical examination of the GI and PI on the same subject by multiple examiners will produce significant variations between evaluations as well as discomfort to the subject.

The Principal Investigator will review the criteria of the GI and PI with the examiner, who will then determine the initial score; after one week, the examiner will again reevaluate the same set of the digital dental photographs in a random order. The two-way random, single measure reliability of the Intraclass Correlation Coefficient (ICC) will be computed and ICC values ≥ 0.85 will signal acceptable calibration of the study examiner.

7. SUMMARY OF STUDY POPULATION DATA

7.1 Subject Disposition

Subject enrollment, including number of subjects screened, number of subjects randomized and the reasons for screen failures, will be summarized by treatment group (if appropriate) and overall.

Subject disposition, including the number and percentage of subjects included in each analysis data set (ITT or PP), as well as reasons for exclusion from the PP data set, will be summarized by treatment group and overall.

Study completion status (completed the study or discontinued early from the study), as well as the primary reason for study discontinuation, will be summarized by treatment group and overall.

7.2 Protocol Deviations

Protocol deviations are any departure from the protocol. Protocol deviations that affect the evaluability of subjects will be reviewed during a blinded review process and documented before data lock and study analysis. Deviations will be summarized by categories, treatment group and overall. Listing of protocol deviations will also be provided.

7.3 Baseline and Demographic Characteristics

Demographic variables will be examined to assess comparability of the treatment groups prior to the initiation of treatment. Characteristics evaluated include age, sex, race, ethnicity and tobacco use status. An overall Fisher's Exact test (discrete variables) or ANOVA model (continuous variables) will be used to compare each demographic or baseline variable among all four treatment groups.

Descriptive summary statistics will be provided for demographic characteristics for each treatment group and overall. For age, the number of subjects, mean, standard deviation, median, minimum and maximum will be provided. For sex, race, ethnicity and tobacco use status, the number and percentage of subjects in each demographic category will be summarized.

In addition, screened subjects participating in the wash-out period before randomization will be summarized by demographic variables.

7.4 Treatment Duration and Oral Rinse Dosing Compliance

Treatment duration will be computed as the number of days from randomization to the last dosing day: (Last Dosing Date-Randomization Date +1). If the last dosing date is missing, the day of last study visit will be used.

The oral rinse compliance will be calculated as a percentage of the documented number of doses taken in the subject diary of the total number of expected doses. The subjects will be expected to take two doses per day unless it is the last day of the treatment period, on which no dose will be expected (based on dosing instruction for PI and GI assessment days). In addition, subjects will be expected to dose for 6 calendar months. For example, subject starting treatment on January 15th will be expected to dose until July 14th with their expected 6-month visit occurring on July 15th.

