5.1 Study Design

This is a prospective, single site, randomized, parallel, blinded clinical trial. Subjects will be randomly assigned to one of four treatment groups identified as Product A, Product B, Product C or Product D.

Subjects will be screened for eligibility and entered into a washout period that is at least 7 days, during which time they will be provided with study toothbrush, toothpaste and dental floss. No oral rinses or medication that alters oral tissue health will be used or taken during the washout period. After randomization, the designated rinse will be placed into a non-transparent container so that other subjects and clinical examiners do not see the allocated rinse per the randomization schedule.

Subjects will be provided with both verbal and written instructions to take home, and a diary for tracking dosing compliance and any side effects from rinse use. Subjects will return the diary along with the empty/used/unused rinse bottles in the original container at their next scheduled visit to monitor for compliance of product use. Subjects that are found to be non-compliant will remain in the study, be re-trained and documented accordingly.

Examinations for the clinical endpoints (PI, GI and BI) will be conducted at the baseline, 3-month (± 10 days), and 6-month (± 10 days) visits.

Interim visits will be scheduled to review diary, replenish study supplies, check study compliance, etc. Subjects will be provided Colgate Regular toothpaste, dental floss and a soft toothbrush (replaced at 3 months) for use during the 6-month study period.

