11.2 Analysis Data Sets

The intent-to-treat (ITT) data set will be the primary dataset and will include ideally all subjects randomized with subjects analyzed in the group to which they were randomly assigned.

A second per-protocol (PP) data set will be defined excluding any subjects with major deviations or lack of compliance with taking their assigned study treatment. These major deviations will be defined in a blinded fashion prior to completion of any analyses and will include violating the PI and GI entry criterion and a compliance of < 80% of planned doses.

All subjects randomized will be included in the safety analyses. In addition, subjects participating in the washout period before randomization will be summarized.

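### Expected doses are fixed at six calendar months while the last visit may fall 10 days either side, so visit date can decide whether a borderline completer stays in the per-protocol set

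*SAP*

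**What the plan says.** SAP 7.4 defines compliance as the "percentage of the documented number of doses taken in the subject diary of the total number of expected doses". Expected doses are "two doses per day unless it is the last day of the treatment period, on which no dose will be expected", and the SAP then adds: "In addition, subjects will be expected to dose for 6 calendar months". Its example is a "subject starting treatment on January 15th will be expected to dose until July 14th with their expected 6-month visit occurring on July 15th". The example covers only a visit held on its scheduled date.

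Protocol 5.1 says the efficacy examinations "will be conducted at the baseline, 3-month (± 10 days), and 6-month (± 10 days) visits". The synopsis and protocol 8.1.6 give the same window for the final visit.

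The score decides membership of the per-protocol (PP) set. Protocol 11.2 excludes subjects with "a compliance of < 80% of planned doses". SAP 5.3, rule (3), joins two wordings with "of planned dose (or alternatively": under 80% of the planned dose, and more than 20% of no rinsing. SAP 5.3 uses the PP set for the comparison with vehicle and for the four-group comparison. SAP 5.2 and 8.1 base the primary analysis on ITT.

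Neither document links the denominator to the actual visit date, caps the doses counted, or says what happens to diary doses recorded after the six-month date. The SAP revision history shows that revision 2 was meant to clarify the compliance computation; the current text still leaves this open.

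**The concern.** The numerator depends on how long the subject was on rinse before the final visit, whereas the denominator assumes that the visit fell on its due date. Two completers who rinse equally well can therefore get different scores because one appointment was earlier than the other, although the protocol permits both dates. Near the 80% limit, the appointment date rather than rinsing behaviour can settle who is in the PP set.

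The two wordings of rule (3) can also disagree for such a subject. A completer seen 10 days early who takes 289 of 342 possible doses has missed 53/342 = 15.5%, inside the 20% allowance for no rinsing. The SAP 7.4 score is 289/362 = 79.8%, which fails the 80% limit.

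At stake is the composition of a supportive analysis set, and a choice that would otherwise be left to whoever programs it.

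**Working it through.** **Inputs.** Two doses per day, none on the final assessment day, and six calendar months expected (SAP 7.4); visit window of 10 days either side (protocol 5.1); PP limit of 80% (SAP 5.3, protocol 11.2).

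**The SAP's example.** January 15 to July 14, both days included, is 181 days in a non-leap year. Expected doses = 2 × 181 = 362. The SAP does not print this total; it follows from the dates.

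**Definitions.** For a visit d days after the due date (negative if early), doses possible = 2 × (181 + d). Real adherence means doses taken divided by doses possible up to the day before the visit. The SAP score is doses taken / 362. The score reaches 80% when real adherence = 0.80 × 362 / [2 × (181 + d)]. Rows for late visits assume that dosing continues to the day before the visit and that all diary doses count.

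| Visit | Doses possible | Score if every dose is taken | Real adherence needed | Score of a subject at 80% real adherence |
|---|---|---|---|---|
| 10 days early | 342 | 342/362 = 94.5% | 289.6/342 = 84.7% | 75.6% |
| 5 days early | 352 | 97.2% | 82.3% | 77.8% |
| On the date | 362 | 100% | 80.0% | 80.0% |
| 5 days late | 372 | 102.8% | 77.8% | 82.2% |
| 10 days late | 382 | 382/362 = 105.5% | 289.6/382 = 75.8% | 84.4% |

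Rounded up to whole doses the limit is 290, and the extremes become 290/342 = 84.8% and 290/382 = 75.9%. Six calendar months spans 181 to 184 days depending on the start date. At 184 days (368 doses, limit 295) the extremes are 295/348 = 84.8% and 295/388 = 76.0%, so the result hardly changes.

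**If doses after the six-month date are not counted.** The late-visit rows no longer apply: no score exceeds 100%, and only the early-visit rows remain.

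**Share of subjects affected.** The documents give no distribution of compliance or of visit dates, so both are assumed. Real adherence is taken as Beta with a standard deviation of 8 to 12 percentage points, and visits as uniform over the 21 days of the window. The share is the average over those days of the probability that adherence lies between 80% and the level needed for that day.

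- Mean compliance 83-88%: about 4-9% reclassified in total. With later doses not counted, about 2-5%, all wrongly excluded.
- Mean compliance 92-95%: about 1-3% in total.

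Visits clustered near the due date would lower these shares. A tighter spread of adherence around a mean close to the limit would raise them.

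**After the change.** With expected doses counted to the day before the actual visit, the denominators are 342, 362 and 382 and the limits 274, 290 and 306 doses. Each is 80.1% of the doses possible.

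**The case against.** **A fixed denominator can be defended.** Both PP rules speak of planned dosing, and the planned course is six months. The share of the planned course taken is a legitimate quantity, different from adherence per day on rinse, and the nominal 80% limit does not itself move. This stands in part: the word reclassified here is relative to the second quantity. For a completer seen within the window, however, the shortfall comes from scheduling that the protocol allows, and SAP 5.3's alternative wording about no rinsing points to behaviour.

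**The late-visit half is inferred.** The SAP does not say that doses after the six-month date count. It also ties the dose-free last day to assessment days, which could be read as the actual visit day. This stands. A reader might infer that late visits certainly inflate the score; the text is silent, so the 105.5% and 75.8% figures are conditional.

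**The fixed denominator guards against short exposure.** The study schedule gives one final column to the 6-month visit and to discontinuation. A subject who rinses perfectly for 91 days and then stops scores 182/362 = 50% under SAP 7.4, but would score 100% if expected doses ended at the last assessment. PP rule (1) removes subjects without 6-month GI and PI values, but the documents do not say whether a discontinuation assessment counts as a 6-month value. This stands and limits the fix.

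**The consequence is small.** This also stands. A reader might infer that the primary result is at risk or that one arm is favoured. Success rests on ITT, allocation is randomised, examiners are blinded, and nothing in the documents links visit date to treatment group.

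**Conclusion.** The point holds, as a minor one. For completers seen within the window, the real adherence needed to stay in the PP set rises to about 84.7% at 10 days early. It falls to about 75.8% at 10 days late only if later diary doses are counted. A fully adherent completer in the window is never excluded, since the lowest possible score is 94.5%; only subjects with real adherence of about 76-85% can change sides.

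The early-visit result rests on the SAP's own rule and calendar arithmetic. The share affected does not: it depends on assumed distributions, and a single misclassification rate should not be read into the plan. No shift in a treatment estimate or p-value has been shown. The effect is confined to the supportive PP analyses, and the ITT primary result and the sample size are untouched.

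**What to change.** In SAP 7.4, for subjects who complete the 6-month visit within its window, define expected doses as 2 × the number of days from first dose to the day before the actual 6-month visit, both days included. Count diary doses over the same days, and use this ratio for PP rule (3). Keep the planned six-calendar-month denominator for subjects who discontinue early, so that a short exposure is not scored as compliant. State which of the two rules applies to a 6-month visit held outside the window.

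The cost is a short addition to the SAP and two denominator rules to program instead of one. The dates needed are already used in the same section for treatment duration. The rule should be settled before data lock, together with the blinded decisions on PP membership.
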